## ANCILLARY REVIEWS

| Which ancillary reviews do I need and when do I need them?
Refer to HRP-309 for more information about these ancillary reviews. |   |   |   |
|---|---|---|---|
| Select yes or no  | Does your study...  | If yes...   | Impact on IRB Review  |
|  Yes
 No  | Include Gillette resources, staff or locations  | Gillette Scientific review and Gillette Research Administration approval is required. Contact: [contact]  | Required prior to IRB submission                                      |
|  Yes
 No  | Involve Epic, or Fairview patients, staff, locations, or resources?   | The Fairview ancillary review will be assigned to your study by IRB staff Contact: [contact]  | Approval must be received prior to IRB committee / designated review. |
|  Yes
 No  | Include evaluation of drugs, devices, biologics, tobacco, or dietary supplements or data subject to FDA inspection? | The regulatory ancillary review will be assigned to your study by IRB staff Contact: [contact]

See: https://policy.umn.edu/research/indide | Consider seeking approval prior to IRB submission .                   |
|  Yes
 No  | Require Scientific Review? Not sure? See guidance on next page.   | Documentation of scientific merit must be provided.
Contact: [contact]  |   |
|  Yes
 No  | Relate to cancer patients, cancer treatments, cancer screening/prevention, or tobacco?                              | Complete the CPRC application process.
Contact: [contact]   |   |
|  Yes
 No  | Include the use of radiation? (x-ray imaging, radiopharmaceuticals, external beam or brachytherapy)                 | Complete the AURPC Human Use Application and follow instructions on the form for submission to the AURPC committee.
Contact: [contact]  | Approval from these committee s must be received                      |

## MEDICAL PROTOCOL (HRP-590)

PROTOCOL TITLE: VISUAL SURROUND SUPPRESSION UNDER PSILOCYBIN

VERSION DATE: May 18, 2023

|  |  |   |   |
|--|--|---|---|
|  Yes
 No | Use the Center for Magnetic Resonance Research (CMRR) as a study location?               | Complete the CMRR pre-IRB ancillary review
Contact: [contact]   | prior to IRB approval;

These groups each have their own application process.   |
|  Yes
 No | Include the use of recombinant or synthetic nucleic acids, toxins, or infectious agents? | Complete the IBC application via eprotocol.umn.edu
Contact:  |   |
|  Yes
 No | Include the use of human fetal tissue, human embryos, or embryonic stem cells?           | Contact OBAO for submission instructions and guidance  |   |
|  Yes
 No | Include PHI or are you requesting a HIPAA waiver?  | If yes, HIPCO will conduct a review of this protocol.
Contact: [contact]  |   |
|  Yes
 No | Use data from the Information Exchange (IE)?   | The Information Exchange ancillary review will be assigned to your study by IRB staff
Contact: [contact]  | Approval must be received prior to IRB approval.

These groups do not have a separate application process but additional information from the study team may be required. |
|  Yes
 No | Use the Biorepository and Laboratory Services to collect tissue for research?            | The BLS ancillary review will be assigned to your study by IRB staff.
Contact: [contact]  |   |
|  Yes
 No | Have a PI or study team member with a conflict of interest?                              | The Col ancillary review will be assigned to your study by IRB staff
Contact: [contact]   |   |
|  Yes
 No | Need to be registered on clinicaltrials.gov?   | If you select "No" in ETHOS, the clinicaltrials.gov ancillary review will be assigned to your study by IRB staff
Contact: [contact]   |   |
|  Yes
 No | Require registration in OnCore?  | If you select "No" or "I Don't Know" in ETHOS, the OnCore ancillary review will be assigned to your study by IRB staff
Contact: [contact] | Does not affect IRB approval.  |

## PROTOCOL COVER PAGE

**MEDICAL PROTOCOL (HRP-590)****PROTOCOL TITLE: VISUAL SURROUND SUPPRESSION UNDER PSILOCYBIN****VERSION DATE: May 18, 2023****REVISION HISTORY**

| Revision # | Version Date | Summary of Changes  | Consent Change? |
|-------------------|---------------------|--|------------------------|
| 1                 | 8/28/2020           | Changed UBACC to the use of the MacCAT-CR  | No                     |
| 2                 | 10/02/2020          | Adding language about video recording all study visits, adding inclusion criteria for wearing face masks/coverings at all times during study visits, description of mixed in-person and Zoom study visits, adding survey screening, and adding e-consenting.   | Yes                    |
| 3                 | 12/09/2020          | Adding information about required COVID testing prior to in-person visits, and adjusting visit schedules for enrolled participants that test positive for COVID prior to a visit to allow for quarantine and reschedule. Also applies to study staff who will also be asked to get tested prior to in-person visits, and adjusting scheduling of visits if quarantine is needed. | Yes                    |
| 4                 | 07/20/2021          | Adding heart rate and respiratory rate data collection during MRI scans  | No                     |
| 5                 | 10/29/2021          | Adding a debriefing session for visits 3a and 5a over zoom (or in person) following each dosing session, adding a follow up EEG and psychophysics measurement during visit 6, updates to how MRI and EEG data will be stored and analyzed, updates to blood draws, and additional devices noted that will be used for data access and analysis, and updates to I/E criteria.     | Yes                    |
| 6                 | 01/14/2022          | Adding additional time for preparatory sessions totaling 8 hours;  | Yes                    |

## MEDICAL PROTOCOL (HRP-590)

## PROTOCOL TITLE: VISUAL SURROUND SUPPRESSION UNDER PSILOCYBIN

VERSION DATE: May 18, 2023

|   |            |   |     |
|---|------------|---|-----|
|   |            | adding 4 additional measures for verbal and visual learning and memory, the adverse childhood experiences questionnaire, and the emotional breakthrough inventory; adding an adapted set of questions to the Matrix reasoning section of the WASI to assess divergent thinking; adjusting total hours in the study to reflect this, and adjusting the compensation to reflect the extra hours; updating the mask mandate for in person dosing visits; creating more structure around staff COVID testing requirements for in-person visits; adding that staff and participants be up-to-date on COVID vaccines, per CDC guidelines; updated language for CMRR MRI usage as updated by the facility.   |     |
| 7 | 11/29/2022 | Adding an administration of the subjective experience questionnaires at the end of the day on each dosing day; Collecting psychophysics and EEG starting at 2 hours into the dosing session, without taking a break between psychophysics and EEG; Extending the time frame for visits 1 and 2 to have some overlap; Participant facing materials for preparation/rapport building; extending the washout time between dosing sessions from 2 weeks to 1 month to account for carry-over effects; Add ECG recording for participants to exclude anyone with a QTc greater than 450 msec, based on the FDA Guidance of Clinical Evaluation of QT/QTc Interval Prolongation and Proarrhythmic Potential for Non-Antiarrhythmic Drugs, collected at baseline, and at the end of the day on each dosing session (visits 2 and 4). | Yes |

**MEDICAL PROTOCOL (HRP-590)****PROTOCOL TITLE: VISUAL SURROUND SUPPRESSION UNDER PSILOCYBIN****VERSION DATE: May 18, 2023**

|   |            |  |     |
|---|------------|--|-----|
| 8 | 01/06/2023 | Reverting to a 2-week washout between dosing sessions due to funders not approving this change. Clarification on hours for preparatory sessions for visits 2 and 4.  | Yes |
| 9 | 05/18/2023 | Updating ICF to include language about potential repeated MRI risks/side effects. Also removing BMI as an exclusion criterion, removing language about COVID safety as the guidelines continue to evolve to reflect that we will adopt the current institutional guidelines to prevent the spread of COVID-19, and updating our phone screen to include more information to help determine ineligibility around mental health symptoms and substance abuse to help with enrollment failures. | Yes |

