### 1.1 Specific Aims:

**Aim 1a will test the acute impact of psilocybin on the strength of the psychophysical surround suppression effect.** Healthy volunteers will complete a visual task at baseline (pre-drug administration) and again after either an oral dose (25mg) of psilocybin or Niacin (100mg) placebo control (baseline, 2 hours post-drug administration, 2 week followup). The psychophysical measurements are made via forced-choice binary (yes/no) responses to questions about participants' perceptions of visual stimuli. The data collected from this Aim will provide a psychophysical characterization of the impact of psilocybin on visual surround suppression.

**Aim 1b will test the acute impact of psilocybin on the strength of known surround suppression-related vERPs measured with EEG.** Neural data will be collected as participants complete the visual tasks in Aim 1a (baseline, 2 hours post-drug administration, 2 week followup). The data collected will provide a neurophysiological characterization of the effect of psilocybin on the target vERPs commonly associated with visual surround suppression.

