We will test two groups for each of these conditions. Group A will be given psilocybin first, and active placebo Niacin second (N=20) and tested on surround suppression and EEG recording starting at 2 hours after ingestion of the experimental compound. Group B will be given niacin on their first dosing day and psilocybin on their second dosing day (N=20) and tested on surround suppression and EEG recording starting at 2 hours after ingestion of the experimental compound.

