**Neuroimaging Procedures.** All brain imaging will be completed at the CMRR on a 3T whole body Siemens MAGNETOM scanner (Siemens Medical Solutions, Erlangen, Germany) using a standard Nova coil. We will take a series of scans during a single session to collect structural and functional fMRI data. Data will be collected from participants during baseline assessment and within 24 hours following each dosing day, and again at 3-4 days and 7 days after each dosing session for a total of 7 scans per participant. After an initial structural scan, we will collect resting state fMRI to test changes in BOLD signal in brain networks known to be impacted by psilocybin and other 5HT2A receptor mediated psychedelics, including the default mode network (Carhart-Harris et al., 2014). Heart rate and respiratory rate data will also be collected during the scan to account for artifacts that may confound results during resting state scan. We will then perform a series of task-based scans using the same visual tasks tested during the EEG dosing session (*SEE Psychophysics section under Visits 2 and 4*). We will then perform a diffusion-weighted MRI (dMRI) scan to look for changes in structural connections in white matter, which has been shown previously in animal models with serotonergic psychedelics (Ly et al., 2018). Data will be processed using standard software packages (e.g., the FMRIB Software Library (FSL - FslWiki)), which is an open-source software library that contains tools for statistical analysis and image processing for MRI brain imaging data).

The same study procedures, except consent, demographics and medical history will be performed at Visits 3, 5, 6 and 7. Pregnancy test will be collected on Visit 1, 2, 3, 4, and 5. EEG and psychophysics will be collected on visits 2, 4, and 6, and fMRI will be collected on Visits 1, 3, and 5. Regarding blood draws, two separate tubes of blood will be collected at Visits 1, 3, and 5 for serum chemistry and cytokine assays.

## VISITS 2 and 4

MEDICAL PROTOCOL (HRP-590)

PROTOCOL TITLE: VISUAL SURROUND SUPPRESSION UNDER PSILOCYBIN

VERSION DATE: May 18, 2023

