**Visits 3 and 5**

**Digital Journal.** Throughout the study, participants will also be asked to keep a digital journal that will be submitted after each dosing session (**Visit 3 and Visit 5**), and at the end of the study (**Visit 7**) to document their qualitative and subjective experience for content analysis. Within 1 week after their dosing session, participants will be asked to write for 30-60 minutes to describe the content of their experience, and any reflections or interpretations they derived from the experience to help determine the subjective information of their drug experience. These will be collected in a REDCap form (see Appendix F) and sent out to participants via email or text after completion of the dosing session, and a follow-up email or text towards the end of the week if they have not completed the form.

**Debriefing session.** One day following each dosing session (Visits 3a and 5a), study staff will meet with the participant for about 60 minutes (either in person at CMRR prior to MRI, or remotely over Zoom) to discuss the dosing session the previous day, and debrief on anything they want to discuss or process with the study staff.

**Blood Draws.** All blood draws will be performed by the clinical staff onsite, and blood samples will be stored at the Cytokine Reference Lab on campus for cytokine assays, and serum chemistry will be processed by Fairview. Samples will be collected at baseline (**Visit 1**) and again at **Visit 3 (a,b,c)** and **Visit 5 (a,b,c)**.

**MRI.** See CMRR section below (5.5).

All neuropsychiatric, baseline and follow up testing will be conducted in the ARC (or Zoom, if appropriate), and all fMRI sessions will be collected at CMRR. All dosing sessions and EEG data collection will be performed in the CRU. The study coordinator will greet each participant upon arrival, and escort them to the different locations for data collection and testing.

MEDICAL PROTOCOL (HRP-590)

PROTOCOL TITLE: VISUAL SURROUND SUPPRESSION UNDER PSILOCYBIN

VERSION DATE: May 18, 2023

Participants will be monitored at each visit for adverse events (*Zoom option*), including for suicidal thoughts, and given at least 2 weeks between dosing/testing sessions for drug washout. After completion of final dosing sessions, participants will undergo follow up assessments at 2 weeks (**Visit 6**) and 2 months after the final dosing session for study closeout (**Visit 7**).

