We will test hypotheses about differences between baseline EEG signal and psychophysics tasks performed under both psilocybin and the active placebo control during the surround suppression task. We will test changes in primary and secondary endpoints between baseline and each of the drug conditions using univariate repeated measures ANOVA, as well as a mixed-effects regression model (random intercept by participant) controlling for additional co-variates such as treatment order, age, sex, and other relevant predictors at baseline that are significantly different between groups. If diagnostic tests reveal poor adherence to model assumptions, equivalent non-parametric tests will be used instead. We will also test changes in resting state fMRI networks from baseline, and 1-day, 3-days and 7-days after exposure to the experimental compound and placebo control. Will use independent component analysis (ICA) to identify functionally meaningful resting state networks using the FMRIB Software Library (FSL). Significance will be tested at  $p < .05$ .

*15.4 Data Integrity:*

Data collection is the responsibility of the clinical trial staff under the supervision of the site PI. The investigator is responsible for ensuring the accuracy, completeness, legibility, and timeliness of the data reported. All information and data collected from and about participants during the research study will be de-identified and kept in the participants folder in a locked cabinet in a locked room accessible only by research staff. Identifiable forms such as screening forms containing DOB and consent forms will be kept separate from participant data. All research staff and volunteers are required to complete data safety and security and HIPAA training according to University of Minnesota policy. All data electronically stored and transferred will be de-identified and any identifiable pieces of information stored electronically will be kept secure accessible by only research staff and will be encrypted if transferred or using secure portal such as Box.

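### Section 15.3 prespecifies no placebo-controlled, carry-over-free estimate of psilocybin versus niacin for the psychophysics and EEG endpoints

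*Combined protocol and SAP*

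**What the plan says.** Section 5.1 describes a two-period crossover with 20 participants per order: Group A takes psilocybin and then niacin, Group B the reverse. Section 1.0 gives the purpose as a comparison with an active placebo. Psychophysics is the primary endpoint (3.1) and EEG the secondary (3.2).

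The operative washout is in section 5.2 (Visits 3 and 5), where participants are "given at least 2 weeks between dosing/testing sessions for drug washout". The Revision History is useful here only for the team's reasoning. Revision 7 records "extending the washout time between dosing sessions from 2 weeks to 1 month to account for carry-over effects". Revision 8 records "Reverting to a 2-week washout between dosing sessions due to funders not approving this change". No passage says that carry-over was ruled out.

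Section 1.1 lists the measurement times as "baseline, 2 hours post-drug administration, 2 week followup". The last of these is Visit 6, 2 weeks after the final dose. Between the doses, participants also meet the tasks in the scanner: "We will then perform a series of task-based scans using the same visual tasks tested during the EEG dosing session" (5.2, Neuroimaging Procedures).

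Section 15.3 tests change from baseline to each drug condition by repeated measures ANOVA, and also fits a random-intercept regression "controlling for additional co-variates such as treatment order, age, sex". It names no first-period estimate, no effect by sequence, no period term, and no use of Visit 6 to look for persistence.

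**The concern.** Only Group A carries psilocybin into its second session. Whatever remains of the psilocybin effect at Visit 4 is scored as niacin in that group, and the psilocybin-minus-niacin difference shrinks. A second route is learning: Group A repeats the tasks in the scanner in the week after psilocybin, Group B in the week after niacin. The documents give no size or direction for this.

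The team itself raised carry-over, so a reader of the results will ask about it. Aim 1a promises a characterization of the drug's impact, so the size of the effect matters as well as its significance. The data for a randomised estimate that avoids the problem will be collected. If that analysis is chosen only after unblinding, it will look selective.

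**Working it through.** **Inputs.** From the documents: 20 per order (5.1); 16 subjects for 92% power (15.2); significance level 0.05 (15.3). Assumed: two-sided testing; the persisting fraction c; the within-person correlation r, the same between any two sessions; no carry-over from niacin.

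**The plan's own figure.** The 92% cannot be reproduced, because section 15.2 gives no numerical effect size, SD or correlation. Solving backwards for a paired two-sided t-test with n = 16 gives a standardised difference dz = 0.90 (0.80 if one-sided). I use 0.90 only as a scale.

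**Bias.** Let D be the true effect and p1, p2 the period effects.
- Group A, psilocybin minus niacin: (p1 − p2) + D(1 − c)
- Group B, psilocybin minus niacin: (p2 − p1) + D
- Mean of the two groups: D(1 − c/2)

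Period cancels in the mean, and an order main effect cancels within each person. Neither term touches c.

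| c | estimate / D | too small by |
|---|---|---|
| 10% | 0.95 | 5% |
| 30% | 0.85 | 15% |
| 50% | 0.75 | 25% |

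Simulation agrees. With 20 per order, r = 0.5 and a period shift of 0.3 SD, the ratio was 0.95, 0.84 and 0.75. A separate run of 150 trials used mixed models with D = 0.90 and c = 50%. The estimate was 0.66 without order, 0.66 with order, and 0.66 with order plus period (expected 0.90 × 0.75 = 0.68). The first period alone gave 0.89, and psilocybin minus baseline gave 0.89.

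**Bias in standard errors.** With all 40 people this is (c/2) × 0.90 × √40.
- c = 10%: 0.05 × 0.90 × 6.32 = 0.28; 95% CI coverage about 94%
- c = 20%: 0.10 × 0.90 × 6.32 = 0.57; coverage about 91%
- c = 50%: 0.25 × 0.90 × 6.32 = 1.42; coverage about 70%

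Power at c = 50% is still 0.986.

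**The order term as a check.** At dz = 0.90 and r from 0.3 to 0.7, its power to show carry-over is 0.05 to 0.06 (c = 10%), 0.06 to 0.07 (c = 20%) and 0.09 to 0.18 (c = 50%).

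**Precision of the first-period comparison.**
- Crossover SE: √(2(1 − r)/40). At r = 0.5 this is 0.16 SD.
- First-period SE with baseline adjustment: √((2/20)(1 − r²)). At r = 0.5 this is 0.27 SD.
- Ratio: √(2(1 + r)), which is 1.61, 1.73 and 1.84 for r = 0.3, 0.5 and 0.7.

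Without baseline adjustment, first-period power at dz = 0.90 with 20 per group is 0.91, 0.79 and 0.58 for the same r.

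**Visit 6 in Group B.** This is 2 weeks after psilocybin, the washout lag. Visit 6 minus baseline has 80% power for dz = 0.66 with n = 20 (0.75 with n = 16). On the assumed scale, 0.66/0.90 means about 73% persistence. It should therefore be read as an estimate with its interval; a non-significant result would not rule out smaller persistence.

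**The case against.** The strongest reply has five parts.

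1. A reader might infer that the trial has no estimate free of carry-over. That goes too far. Psilocybin versus baseline, which section 15.3 does plan, takes no psilocybin carry-over in either order. It has no placebo control, however, and mixes the drug effect with practice and time. Section 15.3 also does not spell out the psilocybin-minus-niacin contrast; it follows from the purpose in section 1.0.

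2. A reader might infer that carry-over would go undetected, or that the 2-week follow-up contradicts the 2-week washout. Neither follows. Visit 6 in Group B can serve as a check of return to baseline. There may also be a measurement before the second dose: 5.2 (Visits 2 and 4) mentions baseline testing of outcome measures and 3.2 mentions EEG before the dosing session, while 5.1 describes one training/baseline session. What is missing is a prespecified use of such data.

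3. A reader might infer that the team judged 2 weeks too short for the task and EEG. Revision 7 names no endpoint, and the trial also follows imaging, blood markers, mood and cognition. Funder non-approval is the only reason recorded, which does not make it the only reason.

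4. No document figure supports any value of c. Sections 4.1 and 13.1 call lasting perceptual changes rare and usually very brief. At c = 10% the bias is about a quarter of a standard error. This stands, and it limits the severity.

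5. It is tempting to call the crossover estimate diluted whenever it falls clearly below the first-period one. That would be a carry-over test under another name. At r = 0.5 the SE of the gap is about √((2/20)((1 + r)/2 − r²)) = 0.22 SD (0.23 in simulation). With D = 0.90 SD the expected gap is 0.90 × c/2 = 0.05, 0.14 and 0.23 SD for c of 10%, 30% and 50%, and simulated power is about 0.05, 0.09 and 0.16. With no carry-over the crossover estimate is the smaller one half the time. The objection is right, and no such rule should be used.

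**Conclusion.** The gap is real but narrow. For psilocybin versus niacin on the psychophysics and EEG endpoints, section 15.3 prespecifies no placebo-controlled estimate free of carry-over, and the order covariate cannot stand in for one. The pooled estimate is D(1 − c/2): 5%, 15% or 25% too small for c of 10%, 30% or 50%. This rests on persistence in the same direction as the acute effect, none from niacin, and assumed values of c. Persistence of this kind pulls the estimate toward zero and widens nothing, so it distorts effect size and interval coverage while leaving significance almost intact at the effect size implied by section 15.2.

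The documents do not show that carry-over occurs on this task, and this point takes no view on the right washout length. It is a cheap improvement to the analysis plan and does not invalidate the crossover.

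**What to change.** Leave the washout and visits as they are. In section 15.3, for both endpoints:

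- State psilocybin versus niacin as a named contrast, and include period in the crossover model.
- Prespecify as a sensitivity analysis the first-period comparison: Visit 2 score, psilocybin-first versus niacin-first, by ANCOVA on the pre-drug baseline plus age group and gender. Report it with a 95% CI beside the crossover estimate, and give the psilocybin-minus-niacin effect by sequence.
- Prespecify Visit 6 versus baseline in Group B, with a 95% CI and the actual lag since psilocybin.
- State that no carry-over test, and no comparison of the two estimates, will decide which result is reported or how it is labelled.

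Two sets of passages must be reconciled. The first is when the pre-drug task and EEG baseline is taken: 3.2, 5.1 and 5.2 (Neuroimaging Procedures, which lists Visits 2, 4 and 6; and Visits 2 and 4) against the Schedule of Events, which also marks EEG at Visit 1. If there is a pre-dose measurement at Visit 4, use it as a further check. The second is the visit windows of 7 to 14 days either way in the Schedule of Events against the minimum interval in 5.2.

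The cost is protocol wording and a few extra models on data already planned, with no new visits or participants. The drawback is precision: the first-period SE is about 1.6 to 1.8 times that of the crossover, so its interval may be too wide to settle the question alone.
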